## **8.2. Exposure and Compliance**

The duration of study drug exposure is defined as the number of days on treatment from the first dose of 402-C-1803 study drug until the last dose of study drug (last dose – first dose + 1). Study drug exposure is summarized by descriptive statistics. Summaries include the total dose (mg) received (based on the number of pills returned), study drug compliance, and duration (days) of

exposure during the study treatment period. In addition, a summary of the number and percentage of patients by dose (5 mg, 10 mg, 20 mg, 30 mg) and by visit window (Section 6.5.4) is generated. If a patient received more than one dose during a visit window, the duration of the longest dose exposure is used to calculate study drug dose during a given visit window.

Total number of doses dispensed and total dose (mg) dispensed is calculated from total number of kits (bottles) recorded on the Study Drug Dispensation electronic case report form (eCRF). Total number of doses received is calculated from information on the eCRF of Study Drug Return and Study Drug Dispensation, as the (total number of doses dispensed – total number of doses returned). Study drug compliance (%) is calculated as  $100 \times \text{total number of doses received} / \text{total number of study days of study participation}$ . For patients who remain on study treatment at the time of an interim or final data cut, the last kit dispensed date is considered the date of last dose. Any dispensation of drug after a subject has his or her end of treatment visit will not be used in any calculation.

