The maximum bardoxolone methyl dose will be determined by proteinuria status based on the ACR value from the eligibility lab assessments from the prior qualifying study, or for patients requiring a screening visit, the maximum bardoxolone methyl dose will be determined based on the ACR values from the screening labs. Patients with eligibility ACR ≤ 300 mg/g will be titrated to a maximum dose of 20 mg, and patients with eligibility ACR > 300 mg/g will be titrated to a maximum dose of 30 mg. Adult patients (≥ 18 years of age) receiving bardoxolone methyl will start with once-daily dosing at 5 mg and will dose-escalate to 10 mg at Week 2, to 20 mg at Week 4, and then to 30 mg at Week 6 (only if eligibility ACR > 300 mg/g) unless

contraindicated clinically and approved by the medical monitor. Patients under the age of 18 enrolling from CARDINAL will start dosing at 5 mg every other day during the first week (from Day 1 through the Week 1 visit) and begin once-daily dosing with 5 mg during the second week of the study (following the Week 1 visit through the Week 2 visit), and then continue with once-daily dosing following the same aforementioned dose-titration scheme based on eligibility ACR at Weeks 2, 4, and 6. Patients under the age of 18 enrolling from FALCON will follow the adult dose titration schedule. Dose de-escalation is permitted during the study if indicated clinically, and subsequent dose re-escalation is also permitted.

All patients in the study will follow the same visit and assessment schedule, as outlined in the study schema (Figure 1). Patients will be scheduled to be assessed in person during treatment at Day 1, Weeks 1, 2, 4, 6, 8, 12, 24, and every 24 weeks thereafter. Patients will also be assessed by telephone contact on Days 3, 10, 21, 31, 38, and 45. If the Day 1 visit for EAGLE is the same as the end-of-study visit from the prior qualifying study, the assessments required for both visits should only be completed once. If the Day 1 visit of EAGLE is not on the same day as the end-of-study visit from prior qualifying study, lab assessments will be performed for Day 1 through the EAGLE central lab.

Figure 1: Schema for Study 402-C-1803

Abbreviations: ACR=albumin to creatinine ratio; D=day; W=week; eGFR=estimated glomerular filtration rate; Scr=screening

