7.3.1. Dose Escalation

Adult patients (≥ 18 years of age) receiving bardoxolone methyl will start with once-daily dosing at 5 mg and will dose-escalate to 10 mg at Week 2, to 20 mg at Week 4, and then to 30 mg at Week 6 (only if eligibility ACR > 300 mg/g) unless contraindicated clinically and approved by the medical monitor. Patients from the CARDINAL study under the age of 18 at the time of consent for participation in the EAGLE study will start dosing at 5 mg every other day during the first week (from Day 1 through the Week 1 visit) and begin once-daily dosing with 5 mg during the second week of the study (following the Week 1 visit through the Week 2 visit), and then continue with once-daily dosing following the same aforementioned dose-titration scheme based on eligibility ACR at Weeks 2, 4, and 6. Patients from the FALCON study under the age of 18 at the time of consent for participation in the EAGLE study will follow the adult dose titration schedule. Dose escalation may proceed slowly if the patient experiences early elevation in ALT/AST over ULN eg, at Week 2 (See Section 9.1.2). The dosing objective is to titrate patients to the maximum dose determined by eligibility ACR and maintain the maximum dose after initial dose-titration. The investigator should discuss any reason for not dose-escalating at Weeks 2, 4, or 6 with the medical monitor.

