7.3.3. Interruption and Resuming of Study Drug

In addition to dose de-escalation and re-escalation, the study drug administration can be interrupted, if clinically indicated. The term interruption refers to a *temporary* halt of study drug administration. If there are any questions regarding study drug interruption, please consult the medical monitor.

Any patient who interrupts study drug for 14 consecutive days or more must have approval from the medical monitor prior to resuming study drug.

When a patient resumes study drug after an extended interruption (eg, more than 14 days), the site should discuss the appropriate starting dose and visit frequency with the medical monitor. The duration of the interruption and the reason for interruption should be taken into consideration when determining how to safely resume study drug.

Following an extended interruption, when the investigator deems it is safe for the patient to return to the site for an in-person visit, the investigator should conduct an evaluation to determine whether the patient is still eligible to receive study drug and to determine the appropriate dose, in consultation with the medical monitor. This should include a confirmation that the patient's circumstances have not changed in a manner that would prohibit administration of the study drug (eg, the patient is now taking an excluded medication). Once the investigator determines study drug administration is appropriate, dosing may proceed.

Patients must have a telephone call approximately 1 week after resuming and an unscheduled, office visit 2 weeks (\pm 3 days) after resuming study drug to perform assessments detailed in Section 9.6.

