9.4. Treatment Compliance

The investigator or his/her designated and qualified representatives will only dispense study drug to patients enrolled in the study in accordance with the protocol. Patients should administer study drug exactly as instructed by the site. Non-compliance is defined as taking less than 80% or more than 110% of expected study medication during any evaluation period (visit to visit). A lack of treatment compliance during any evaluation period (visit to visit) should be entered as a protocol deviation.

Patients should record in the patient diary all administered and missed doses of study drug. A missed dose includes inadvertent missed doses as well as study drug interruptions and discontinuations. Patients will be asked to return all unused study drug (study drug bottles and any unused capsules). The study drug must not be used for reasons other than that described in the protocol.

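### SAP 8.2 divides doses received by study days, not expected doses, so read literally it understates compliance for adherent patients who have days with no dose due

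*SAP*

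**What the plan says.** SAP 8.2 takes doses received as "total number of doses dispensed – total number of doses returned" and expresses compliance as 100 times that number over the "total number of study days of study participation". The SAP does not define participation and makes no adjustment for days without a scheduled dose. The same section defines an on-treatment duration, "last dose – first dose + 1", but uses it for exposure and not as the compliance denominator.

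Protocol 9.4 uses a different reference quantity, expected medication per interval between visits: "Non-compliance is defined as taking less than 80% or more than 110% of expected study medication during any evaluation period (visit to visit". On what goes in the patient diary, the same section adds: "A missed dose includes inadvertent missed doses as well as study drug interruptions and discontinuations".

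Several provisions create days on study without a dose:

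- **Alternate-day week.** CARDINAL patients under 18 "will start dosing at 5 mg every other day during the first week" (Protocol 7.1, repeated in 7.3.1).
- **After the last dose.** Patients leaving before commercial availability complete End of Study within 30 days of discontinuation if possible (Protocol Table 5, footnote b). SAP 6.5.4 sets a follow-up window of 14 to 35 days after last dose.
- **Before the first dose.** Study day is counted from first kit dispensation, which the SAP acknowledges can come before the first dose (SAP 6.5.2).
- **Interruptions.** Under Protocol 7.3.3, "the study drug administration can be interrupted, if clinically indicated". Protocol 9.1.1, 9.1.2, 9.1.9 and Appendix 1 direct interruptions in specified situations.

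SAP Section 2 says the SAP prevails over the protocol on planned analyses, and Protocol 12.3 agrees.

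**The concern.** The two documents use the word compliance for different quantities, and the SAP's version is the one that will be programmed. A ratio of doses to calendar days equals adherence only when one dose is due every day. Where that fails, the percentage mixes three things: what the patient chose to do, what the regimen required, and how long the patient stayed on study without drug.

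The study is open-label with no comparator, and compliance is one of its planned exposure summaries. A reader who sees a low value cannot tell skipped doses from a scheduled non-dosing day or a wait for the final visit. Off-drug tails may not be confined to early withdrawals: SAP Section 2 records a study drug termination date of 10 May 2023, so patients still on drug at that date could also accrue days between last dose and End of Study.

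**Working it through.** The plan states no compliance figure, so there is none to reproduce. The check applies the SAP formula to a patient who takes every prescribed dose.

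**Inputs**

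- Numerator and denominator: SAP 8.2, with participation read literally as days in the study.
- Alternate-day week: Protocol 7.3.1. Assumed dosing on Days 1, 3, 5 and 7, so 4 doses and 3 non-dosing days.
- Off-drug tail F: 30 days (Protocol Table 5, footnote b), with 14 and 35 days (SAP 6.5.4) as the range.
- Interruption length I: the documents give no lengths or frequencies. 14 and 42 days are assumptions.
- Dispensation-to-first-dose gap: no length is given, so it is not quantified. It acts in the same way as a tail.
- All unused drug is assumed returned, and a 30 mg dose (two 15 mg capsules, Protocol 10.1) is counted as one dose.

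**Off-drug tail alone: T / (T + F), with T days on drug**

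| T | F = 14 | F = 30 | F = 35 |
|---|---|---|---|
| 84 | 84/98 = 85.7% | 84/114 = 73.7% | 84/119 = 70.6% |
| 168 | 168/182 = 92.3% | 168/198 = 84.8% | 168/203 = 82.8% |
| 336 | 336/350 = 96.0% | 336/366 = 91.8% | 336/371 = 90.6% |

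With F = 30 the result is below 80% only if T is under 4 × 30 = 120 days.

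**Alternate-day week alone: (T − 3) / T**

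- Day 14: 11/14 = 78.6%
- Week 4: 25/28 = 89.3%
- Week 24: 165/168 = 98.2%
- Week 48: 333/336 = 99.1%

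The result is below 80% only if participation ends before Day 15.

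**Interruption alone: (T − I) / T**

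- 14 days: 154/168 = 91.7%; 322/336 = 95.8%
- 42 days: 126/168 = 75.0%; 294/336 = 87.5%

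The result is below 80% only if T is under 5 × I.

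**Combined: 3 alternate-day skips, a 14-day interruption and a 30-day tail**

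- 168 treatment days: (168 − 3 − 14) / (168 + 30) = 151/198 = 76.3%
- 336 treatment days: 319/366 = 87.2%
- 672 treatment days: 655/702 = 93.3%

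**Same 168-day patient with doses expected from first to last dose as the denominator**

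- Interruption days not expected: 151/151 = 100%
- Interruption days counted as missed: 151/165 = 91.5%

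The gap between these last two figures is the part that Protocol 9.4 leaves open. The fall from 91.5% to 76.3% comes only from the alternate-day week and the tail.

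**The case against.** The case for leaving this alone has five parts.

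1. **Interruptions.** Protocol 9.4 tells patients to record interruptions as missed doses and nowhere removes directed ones from expected medication. A reader might infer that the SAP contradicts the protocol by penalising safety holds. The documents do not support that; they leave the question open. This stands. The alternate-day week and off-drug days do not depend on it.

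2. **The tail is an inference.** Participation is undefined, SAP 8.2 introduces these summaries as covering the treatment period, and Protocol 8.5 treats discontinuation as stopping drug and visits together. An on-treatment reading is therefore possible and would remove the tail. This stands in part. Protocol 8.5 still asks for an End of Study visit after permanent discontinuation. SAP 8.2 also has an explicit first-to-last-dose duration that it did not use here, so the literal reading is the natural one. The alternate-day shortfall remains on either reading.

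3. **The effect fades.** The lowest values need short participation, long interruptions or a combination. This is a long-term extension, and nothing shows that short durations are typical. This stands.

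4. **Nobody is labelled.** A reader might infer that adherent patients will be classed as non-compliant. SAP 8.2 applies no 80% or 110% cut-off, and deviations are entered per visit interval under Protocol 9.4, separately from this whole-study percentage. This stands.

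5. **Little depends on it.** Compliance is not an endpoint, no analysis population is defined by it, and duration, total dose and dose by visit window are reported alongside. This stands, and it limits the importance of the point.

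**Conclusion.** The point holds as a defect in a descriptive summary. The stated formula uses study days where the protocol uses expected medication, and because the SAP governs, the protocol definition does not correct it. For a fully adherent patient, each kind of day without a dose due can only lower the result.

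The size ranges from negligible to material. The alternate-day week costs 3 doses in one small subgroup, under 2 percentage points by Week 24. A 30-day tail costs about 26 points after 84 days on drug, 15 after 168 and 8 after 336. These figures assume the literal reading of participation, the stated tail and dosing days, and complete drug return. If unused drug is not returned it counts as received, which would push the figure the other way.

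Two stronger conclusions might be drawn and should not be. One is that long-term participants will generally fall below 80%; the arithmetic shows this needs short follow-up, long interruptions or both. The other is that a safety conclusion is compromised; no endpoint, population or test uses compliance. What remains is a published percentage that does not measure what its name says.

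**What to change.** Replace the denominator in SAP 8.2 so that compliance is 100 × doses taken / doses expected. Doses expected are those prescribed from first to last dose, the exposure period already defined in that section, with Week 1 counted on the alternate-day schedule for CARDINAL patients under 18. This removes days before the first and after the last dose without needing a definition of participation.

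Reconcile SAP 8.2 with Protocol 9.4 on whether directed interruptions count against compliance, and state the answer in the SAP. Where interruption dates are in the database, present compliance both with and without those days.

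The cost is a sentence or two in the SAP and a small extra derivation. The limit is data. SAP 8.2 names only the dispensation and return forms, and missed doses go in the patient diary, which the documents do not say is entered in the database. The interruption split therefore depends on which dates the eCRF captures. The change of denominator itself needs only first and last dose dates and the prescribed schedule.

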10.4. Study Drug Administration

Please refer to Section 9.9.9 for details on study drug administration. It is the responsibility of the investigator or designee to provide clear instructions to the patient regarding the number and

type of capsules to be ingested at each study drug administration time point listed in [Table 5](#). Patients must be instructed to continue taking study drug once daily unless: (1) the patient has been otherwise instructed by the investigator or (2) the patient has been formally discontinued from study treatment.

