#### 6.5.4. Visit Windows

**Table 2: Visit Window (Days)**

Analysis Visit	Label	Target Study Day	Analysis Window
0	Day 1	1	1
1	Week 1	7	$2 \leq \text{Study Day} \leq 10$
2	Week 2	14	$11 \leq \text{Study Day} \leq 21$
4	Week 4	28	$22 \leq \text{Study Day} \leq 35$
6	Week 6	42	$36 \leq \text{Study Day} \leq 49$
8	Week 8	56	$50 \leq \text{Study Day} \leq 70$
12	Week 12	84	$71 \leq \text{Study Day} \leq 126$
24	Week 24	168	$127 \leq \text{Study Day} \leq 210$
48	Week 48	336	$308 \leq \text{Study Day} \leq 364$
72	Week 72	504	$476 \leq \text{Study Day} \leq 532$
96	Week 96	672	$644 \leq \text{Study Day} \leq 700$
120, 144, etc.	Week 120, Week 144, Every 24 Weeks Thereafter	Analysis Visit $\times$ 7	$([\text{Analysis Visit} \times 7] - 28) \leq \text{Study Day} \leq ([\text{Analysis Visit} \times 7] + 28)$
FU	Follow-up	28 days after last dose	$14 \leq \text{Days after last dose}^a \leq 35$

a For safety analyses, last dose for patients completing the treatment or permanently discontinuing study drug that occur on the date of last dose or less than 14 days after last dose are considered on treatment.

The safety follow-up is based on days since last dose. If more than one assessment exists during the follow-up after last dose, the one closest to 28 days following the date of the last study drug administration is used for analysis and summary.

If a parameter is assessed or measured more than once within a visit window, the one that is closest to the protocol-scheduled time point (or target study day) is used for the purposes of data analysis and summary. If two assessments are equidistant from a target study day, the earlier assessment is used. If the visit used for analysis includes two assessments on the same day, the average of assessments will be used for non-laboratory parameters. For laboratory parameters, if both an original and retest result are available in the laboratory dataset, the original result will be used and the second (ie, “retested”) result will be ignored. Records from visits not closest to the target study day, and therefore not used in analyses, are presented in by-subject data listings.

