#### **6.6.3. Missing Start and Stop Dates for Adverse Events**

Treatment-emergent adverse events (TEAEs) are events that either:

- Had a date of onset on or after the date of the first dose of study drug and not more than 30 days after the date of the last dose of study drug, or
- Had no recorded date of onset with a stop date after the first dose of study drug, or
- Had no recorded date of onset or stop date.

Adverse events with incomplete start dates are considered after the date of first dose if:

- Day and month are missing, and the year is equal to or after the year of the first date of study drug administration;
- Day is missing and the year is after the year of the first date of study drug administration;

- Day is missing and the year is equal to the year of the first date of study drug administration and the month is equal to or after the month of the first date of study drug administration; or
- Year is missing.

Adverse events with incomplete start dates are considered on or within 30 days of last dose, if:

- Day and month are missing, and the year is equal to or before the year of the date of last dose of study drug plus 30 days;
- Day is missing and the year is equal to or before the year of the date of last dose of study drug plus 30 days, and month is equal to or before the month of the date of last dose of study drug plus 30 days;
- Year is missing.

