#### **6.6.4. Missing End of Treatment Date**

For patients without a full end of treatment date (i.e., missing day, month, or year), the last study drug dispensation date will be used as the end of treatment date for purposes of analysis.

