### 8.1. Adverse Event Preferred Term and Body/Organ System Summary Tables

Adverse events are summarized by treatment as defined by the safety analysis set. General considerations for AE summaries and calculations are:

- Multiple events by PT and SOC are counted once only per patient for summaries of AE incidence.
- For summaries of AE incidence by severity, only the most severe event is counted per patient.
- For summaries of AE incidence by relationship, only the most related event is counted per patient.
- An AE with a missing resolution date or incomplete date that is not identified as continuing is assumed to be continuing and no duration is calculated.
- Only TEAEs are included in summaries.

Adverse events are coded using MedDRA version 21.1. In MedDRA, each verbatim term is mapped to a PT and high-level term, which is then mapped to an SOC. Tables and listings will present data at the SOC and PT level.

Treatment emergent adverse events (TEAEs) are events that either:

- Have a date of onset on or after the date of the first dose in the 402-C-1803 study and not more than 30 days after the date of the last dose of study drug in the 402-C-1803 study, or
- Have no recorded date of onset with a stop date after the first dose of study drug, or
- Have no recorded date of onset or stop date

Adverse events with a date of onset in a prior study that continued during the 402-C-1803 study are not considered TEAEs.

In addition, AEs that occurred >30 days after the date of last dose of study drug are summarized as late-onset AEs. These are AEs that had a date of onset more than 30 days after the date of the last dose of study drug in 402-C-1803 study.

The investigator grades the severity of the AEs as mild, moderate, or severe as defined in the study protocol Section 11.5. The investigators graded association or relatedness to the study medication according to criteria specified in Section 11.4 of the study protocol.

As defined in the protocol, an SAE is an AE that results in any of the following:

- Death;
- A life-threatening adverse drug experience;
- Patient reaches ESKD (defined as the initiation of maintenance dialysis for 12 weeks or more or kidney transplant)
- Inpatient hospitalization or prolongation of existing hospitalization;
- Results in persistent or significant incapacity or substantial disruption of the ability to conduct normal life functions;

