### **8.4.2. Categorical Summaries of Laboratory Results**

The number and percentage of patients by laboratory normality and abnormality categories at any time during the study (Normal, Low, High) are summarized by treatment analysis group (Section 4.5), laboratory category (hematology, chemistry, and urinalysis), and laboratory test. The worst abnormality values are defined as the maximum values while on study treatment (ie, up to < 14 days after last dose), except for magnesium and hemoglobin. The worst abnormal values for magnesium and hemoglobin are defined as the minimum values while on study treatment.

An initial set of parameters of specific interest (ALT, AST, ACR) are summarized using shift tables, though additional parameters may be added as appropriate. Shift tables summarizing (1) baseline to end of treatment, and (2) baseline to worst on-treatment, (3) baseline to follow-up, and (4) worst on-treatment to follow-up are presented for lab parameters as appropriate. For ACR, summaries will present shifts from/to the categories in Section 6.5.7.1. For ALT and AST, summaries will present shifts from/to the following categories:

- $< 3 \times$  upper limit of normal (ULN)
- $\geq 3 \times$  ULN to  $< 5 \times$  ULN
- $\geq 5 \times$  ULN to  $< 10 \times$  ULN
- $\geq 10 \times$  ULN to  $< 20 \times$  ULN
- $\geq 20 \times$  ULN

In addition, a summary table is provided by treatment analysis group (Section 4.5) for the number and percentage of patients meeting a following pre-specified threshold level at any time during the study:

- ACR  $> 3500$  mg/g
- Magnesium  $< 1.3$  mEq/L (0.65 mmol/L)
- BNP  $> 200$  pg/mL
- N-terminal prohormone BNP  $> 1000$  pg/mL

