#### **8.4.2.2. Frequency of End Stage Kidney Disease, eGFR decline $\geq 30\%$ , or eGFR $< 15$**

The kidney failure composite outcome is defined as reaching one of the following:

- 30% decline from baseline in eGFR; or
- eGFR  $< 15$  mL/min/1.73 m^2; or
- ESKD (initiation of maintenance dialysis or kidney transplant).

A  $\geq 30\%$  decline or eGFR  $< 15$  is considered confirmed when the threshold is achieved at  $\geq 2$  visits. Patients who achieved the threshold at their last visit, and did not have a second confirmatory visit, are considered confirmed. The analysis uses initiation of maintenance dialysis or kidney transplant as reported prior to the end of the follow-up window in the database by the investigator. Any initiation of maintenance dialysis or kidney transplant that occurs after the follow-up window will be listed separately. Patients with a decrease from baseline in eGFR of  $\geq 30\%$  at the last on-treatment visit will be considered to have a  $\geq 30\%$  decrease from baseline eGFR. In the event a patient has both an increase from baseline in eGFR of  $\geq 30\%$  and a decrease from baseline in eGFR of  $\geq 30\%$ , only the decrease from baseline will be considered in composite endpoint analyses.

The proportion of patients with ESKD (dialysis/transplant), eGFR decline  $\geq 30\%$ , or eGFR  $< 15$  will be summarized, and the composite of all these criteria will be evaluated. The frequency analyses will be performed for all visits. No off-treatment eGFR values are included in the analysis.

As a sensitivity analysis, the analyses are repeated for the frequency of patients with ESKD (dialysis/transplant), eGFR decline  $\geq 30\%$ , or eGFR  $< 15$  with all-cause death added to the kidney failure composite.

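### SAP 6.6.4 and 8.2 date the end of dosing at the last dispensing visit, which usually understates exposure duration by up to about 168 days, and the SAP does not say whether that date also sets the safety windows

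*SAP*

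**What the plan says.** Two SAP rules substitute a dispensing date for the end of dosing.

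- **SAP 8.2 (Exposure and Compliance).** For patients still on treatment at an "interim or final data cut, the last kit dispensed date is considered the date of last dose". The same section defines exposure as last dose minus first dose plus 1.
- **SAP 6.6.4.** If the day, month or year of the end-of-treatment date is missing, "the last study drug dispensation date will be used as the end of treatment date for purposes of analysis".

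Other rules count from last dose without referring to either section.

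- **SAP 8.1:** "AEs that occurred >30 days after the date of last dose of study drug are summarized as late-onset AEs", and only treatment-emergent events enter the other AE summaries.
- **SAP 8.4.2:** the worst laboratory value is taken from the "maximum values while on study treatment (ie, up to < 14 days after last dose"; minimum values are used for magnesium and hemoglobin.
- **SAP Table 2:** the follow-up window runs from 14 to 35 days after last dose. Footnote a defines on-treatment by reference to "last dose for patients completing the treatment or permanently discontinuing study drug".
- **SAP 8.4.2.2:** "Any initiation of maintenance dialysis or kidney transplant that occurs after the follow-up window will be listed separately".

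On dosing, Protocol 10.4 sets the default: "Patients must be instructed to continue taking study drug once daily unless" the investigator has said otherwise or treatment has been formally discontinued. Protocol 9.9.10 has drug dispensed on Day 1, at Weeks 2, 4, 6, 8, 12 and 24, and every 24 weeks after that.

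**The concern.** A dispensing date normally marks the start of a supply. Using it as the end of dosing drops the days on which that supply was taken, and exposure duration is the context in which the safety tables are read.

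6.6.4 also discards information. A patient whose stop month and year are on file, with only the day missing, is still moved back to the last dispensing visit. SAP 6.6.3 handles partial AE onset dates differently and uses what is known: one of its conditions is that the "month is equal to or before the month of the date of last dose of study drug plus 30 days". That section classifies events and does not impute a date, so it is a contrast in approach rather than a contradiction.

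The second issue is a gap. AE and SAE frequency belongs to the primary endpoint, and treatment-emergent status depends on last dose. 8.2 speaks of the date of last dose but sits in the exposure section. 6.6.4 speaks of an end-of-treatment date, which the SAP never equates with last dose, yet applies it for analysis generally. Two programmers could reasonably build different treatment-emergent counts from the same data.

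**Working it through.** The plan gives no exposure figure to reproduce, so this is date arithmetic.

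**Inputs.** Dispensing every 24 weeks after Week 24 (Protocol 9.9.10); visit tolerance ±3 days (Protocol Table 5); once-daily dosing (Protocol 10.4); exposure = last dose − first dose + 1 (SAP 8.2). Assumption: the cut or stop falls uniformly within the dispensing interval.

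**Size of the gap.**
- Nominal interval: 24 × 7 = 168 days.
- Longest with both visits in window: 168 + 3 + 3 = 174 days.
- Mean shortfall: 168 / 2 = 84 days.
- Before Week 24 the longest scheduled interval is 84 days (Week 12 to Week 24).
- Bottles hold 30 or 90 capsules (Protocol 10.2), and partial supplies are allowed, with 3 months as the protocol's example. A 90-day supply gives a mean shortfall of 45 days; a 30-day supply gives 15.

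**Worst case under 8.2: cut on the day before the next dispensing, first dose on Day 1.**

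| True exposure (days) | Recorded (days) | Lost (days) | Lost (%) |
|---|---|---|---|
| 335 | 168 | 167 | 49.9 |
| 503 | 336 | 167 | 33.2 |
| 671 | 504 | 167 | 24.9 |
| 839 | 672 | 167 | 19.9 |

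**Mean relative loss per patient.** With k completed 24-week cycles at the last dispensing, it is 1 − k × ln((k+1)/k):
- Weeks 24–48 (k = 1): 1 − ln 2 = 30.7%
- Weeks 48–72 (k = 2): 18.9%
- Weeks 96–120 (k = 4): 10.7%

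**6.6.4 with only the day missing.** Taking 1461 dispensing dates (four calendar years) and stop offsets of 0 to 167 days, the dispensing-date rule errs by 83.5 days on average (maximum 167). Using the last day of the known month errs by 14.7 days on average (maximum 30).

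**Conditional check: only if the substituted dates also drive the windows.** With gap G uniform on 0 to 168 days, on-drug days after dispensing total ΣG = 168 × 169 / 2 = 14196.
- Beyond the 30-day limit: (138 × 139 / 2) / 14196 = 9591 / 14196 = 67.6%
- At or beyond 14 days: 12090 / 14196 = 85.2%
- Beyond 35 days: 8911 / 14196 = 62.8%
- Beyond 30 days with a 90-day supply: 1830 / 4095 = 44.7%; with a 30-day supply: none

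These are shares of days, not of events or samples. As an illustration under 6.6.4, suppose a patient stops 150 days after dispensing and gives end-of-study samples 5 days later. The samples are truly on treatment (under 14 days). Counted from dispensing they fall at day 155, outside both the on-treatment and the follow-up windows.

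**The case against.** The strongest reply is about reach, and much of it stands.

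- **8.2 may have little left to act on.** The SAP records the decision to end development, communicated to sites on 10 May 2023, and SAP 5.2 places the final analysis after the last patient completes. Patients still dosing would then arise only at another interim lock. SAP 2 and 5.1 still provide for such locks, with all outputs and an interim report, but call the results preliminary.
- **The bias is not strictly downward.** Protocol 7.3.3 allows interruptions. A patient who stopped before the last dispensing, or never opened that kit, has exposure overstated.
- **The dispensing date is a recorded, cautious anchor.** That is a fair defence where nothing else is known. It does not justify ignoring a known month and year.
- **The consequences are descriptive.** There is no formal testing, and SAP 6.2 bases AE percentages on treated patients, so the exposure error alone does not change them.

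A reader might infer that most on-drug AEs after the last dispensing are lost. The documents do not support that. No text links 8.2 or 6.6.4 to the AE window, and footnote a to Table 2 can be read as excluding ongoing patients. Even if the link held, the events would move to the late-onset summary and stay in the listings.

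A reader might also infer wide misclassification of laboratory data. From Week 24, scheduled samples are taken at the dispensing visits, so mainly unscheduled and end-of-study samples would be exposed.

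Nor do the documents show that kidney failure events would drop out at a cut. Under Protocol 8.5 and 9.1.9, transplant or confirmed maintenance dialysis ends treatment and the date is documented, so 8.2 hardly reaches those patients. What remains is dialysis not yet confirmed at 12 weeks, or an incomplete date under 6.6.4; such a patient may still count through the eGFR criteria.

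**Conclusion.** The point holds for exposure duration and should be fixed. Both rules put the end of dosing at the start of the last supply. The usual result is understatement, nominally by up to 168 days and by about 84 days on average for an affected patient on the 24-week cycle. That average rests on a uniform stop or cut and a full 24-week interval; partial or unscheduled dispensing reduces it, visit windows can stretch the maximum to 174 days, and an earlier interruption can reverse the sign. 6.6.4 is the limb that survives to final lock, but the number of patients with an incomplete date is not given and may be small.

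The effect on the treatment-emergent, on-treatment and follow-up windows is an omission in the SAP, not a demonstrated error. The day shares above describe what would follow under one reading, so confidence in that part is only moderate.

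**What to change.** 1. **SAP 6.6.4.** When month and year are known, impute the latest compatible date, bounded by death, last contact and end of study. Use the dispensing date only when no usable month and year exists.
2. **SAP 8.2.** For patients still on treatment at a cut, end exposure at the last confirmed dosing date or, failing that, at the data-cut date. Diaries record doses taken and missed (Protocol 9.4), which gives a source. The confirmation should post-date the last dispensing; one made at that visit would simply reproduce the present rule.
3. **SAP 6.5.4, 8.1 and 8.4.2.** State that windows counted from last dose apply only to patients who have stopped treatment, and which last-dose date feeds them, including whether the date imputed under 6.6.4 does.

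The cost is SAP wording and one date derivation. The downside is possible overstatement: at most 30 days where the stop month is known, and up to the open supply (nominally 168 days) where the cut date is used for a patient who stopped unnoticed.
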